3.1.5 Handling of missing data

No imputation for missing efficacy endpoints will be done. Repeated measures mixed effect model (MMRM) will be used which, in the event of missing data, uses all data that are available.

Laboratory values of the form “<x” (ie below the lower limit of quantification) will be imputed as “0.5x LLOQ” in the calculation of summary statistics but displayed as “<x” in the listings. No imputation will be done for laboratory values of the form “>x” (ie above the upper limit of quantification) and the value “>x” will be displayed in the listings. Note that 0 should not be used as an imputed value in case the endpoint requires a log transformation.

Additionally, adverse events that have missing causality (after data querying) will be assumed to be related to study drug.

For missing ADA data, no imputation is planned.

PK plasma concentrations below the lower limit of quantification will be reported as NQ (Not Quantifiable) in the listings with the LLOQ defined in the footnotes of the relevant TFLs. Individual PK plasma concentrations that are Not Reportable will be reported as NR and those that are missing will be reported as NS (No Sample) in the listings. PK plasma concentrations that are BLQ, NR or NS will be handled as follows for the provision of descriptive statistics:

- Any values reported as NR or NS will be excluded from the summary tables and corresponding figures.

- At a time point where less than or equal to 50% of the concentration values are BLQ, all NQ values will be set to the LLOQ, and all descriptive statistics will be calculated accordingly.
- At a time point where more than 50% (but not all) of the values are BLQ, the gmean, gmean \pm gSD and gCV% will be set to NC (Not calculable). The maximum value will be reported from the individual data, and the minimum and median will be set to BLQ.
- If all concentrations are BLQ at a time point, no descriptive statistics will be calculated for that time point. The gmean, minimum, median and maximum will be reported as BLQ and the gCV% and gmean \pm gSD as NC.
- The number of values below LLOQ ($n < \text{LLOQ}$) will be reported for each time point together with the total number of collected values (n).

Three observations $>$ LLOQ are required as a minimum for a PK plasma concentration to be summarised. Two observations $>$ LLOQ are presented as minimum and maximum with the other summary statistics as NC.

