3.1.3 Absolute, relative and percent change from baseline

Absolute and percent change from baseline will be derived as follows:

$$\text{Absolute change from baseline outcome variables} = (\text{post-randomisation value} - \text{baseline value}).$$

$$\text{Percent change from baseline} = ((\text{post-randomisation value} - \text{baseline value}) / \text{baseline value}) \times 100.$$

For variables log normally distributed, the relative change from baseline is calculated as the visit log transformed value minus the baseline log transformed value.

If either the post-randomisation value or the baseline value is missing, then the changes from baseline value will also be set to missing.

Percentage change from baseline will not be calculated for participants where the result at baseline is 0.

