3.1.7 Derivation of subgroups

Following subgroups will be explored. Any participants with a missing value for the defined subgroup will be excluded from the analysis of that subgroup. Subgroups will only be explored if there is at least 20% of the total participants in that subgroup.

- Gender (male vs female);

- Age by category (≥ 18 to < 50 vs ≥ 50 to < 65);
- Race (as entered in the eCRF);
- BMI (< 19 kg/m², ≥ 19 - < 25 kg/m², ≥ 25 - < 30 kg/m², ≥ 30 kg/m²);
- Geographical region (North America [USA], South America [Argentina], Eastern Europe [Hungary, Poland], Western Europe/Rest of the World [Germany, UK, South Africa]);
- Baseline percent predicted pre-bronchodilator FEV₁ ($< 60\%$ vs $\geq 60\%$);
- Age of asthma onset ($<$ median vs \geq median);
- Number of exacerbations in last 12 months as collected in eCRF (1 vs ≥ 2);
- Smoking status at baseline (never vs former);
- Baseline total ACQ-6 ($<$ median vs \geq median);
- Baseline total SGRQ ($<$ median vs \geq median);
- Baseline ICS total daily dose (< 500 μ g vs ≥ 500 μ g);
- Baseline blood eosinophils ($< 0.3 \times 10^9$ L vs $\geq 0.3 \times 10^9$ L);
- Background medication use (dual therapy vs triple therapy);
- Baseline FeNO (< 25 ppb vs ≥ 25 ppb);
- Baseline Total IgE (≤ 100 kU/L vs > 100 kU/L);
- Baseline mono or poly sensitised to allergen (IgE) (multiple allergens sensitisation vs single allergen sensitisation);
- T2 Corren (high vs low);
- T2 GINA (high vs low);
- SARS-CoV-2 PCR test (positive at any point vs never positive);
- SARS-CoV-2 Serology test (negative at baseline and positive at end of study vs all others);

- CCI [REDACTED]

[REDACTED]

[REDACTED]

[REDACTED]

[REDACTED]

Background medication use

Triple therapy will be defined as the combination of inhaled corticosteroids, long-acting beta-agonist and long-acting anti-muscarinic agent (ICS + LABA + LAMA). Dual therapy will be defined as ICS + LABA.

Allergen sensitisation

For the allergen specific IgE with a qualitative (positive or negative) result, a positive result and total IgE >100 kU/L will define sensitisation. For the allergen specific IgE with a quantitative result, a result equal or greater than 1.41 kU/L and total IgE > 100 kU/L will define sensitisation.

GINA T2 cut-offs

High T2 will be defined as a baseline eosinophil count of $\geq 0.15 \times 10^9$ L and/or elevated baseline FeNO (≥ 20 ppb) and/or at least one allergen sensitisation at baseline.. Other cases will correspond to Low T2.

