4.2.7.6 Other safety tests

NT-proBNP results will be summarised with descriptive statistics at each visit and change from baseline summarised for each post-baseline visit for the As-treated population. NT-proBNP results will be also summarised in shift tables comparing maximum value during treatment with baseline value for the As-treated population.

The number of subjects tested positive for SARS-CoV-2 (by PCR or serology test) at end of study, but who were tested negative at baseline visit will also be presented.

Finally, the number of subjects tested positive for SARS-CoV-2 (by PCR or serology test) during the study (including both intervention and follow-up periods) who experienced or not at least one COVID-19 related AEs/SAEs will be provided.

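### Laboratory results above the upper quantification limit are given no numeric value, so read literally the SAP leaves the highest results out of numeric summaries, log-scale biomarker models and numeric maxima

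*SAP*

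**What the plan says.** SAP section 3.1.5 (Handling of missing data) treats the two ends of the assay range differently.

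- **Below the lower limit:** results of the form `<x` "will be imputed as “0.5x LLOQ” in the calculation of summary statistics but displayed as “<x” in the listings".
- **Above the upper limit:** "No imputation will be done for laboratory values of the form “>x” (ie above the upper limit of quantification". The only use then given is that "the value “>x” will be displayed in the listings".

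No sentence says how a `>x` result enters a summary, a model, a maximum or a category. Two other rules act on values that are absent:

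- Section 3.1.3: "If either the post-randomisation value or the baseline value is missing, then the changes from baseline value will also be set to missing".
- Section 3.1.7: "Any participants with a missing value for the defined subgroup will be excluded from the analysis of that subgroup".

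Several outputs draw on these laboratory values:

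- Section 4.2.8.2 has descriptive summaries and log-scale models for total IgE, EDN, sST2, IL-5, IL-13 and TSLP.
- Section 4.2.7.6 has NT-proBNP descriptive statistics by visit, and "NT-proBNP results will be also summarised in shift tables comparing maximum value during treatment with baseline value for the As-treated population".
- Section 4.2.7.3 has liver plots in multiples of the upper limit of normal, and a table of maximum ALT and AST by maximum bilirubin.

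**The concern.** A result reported only as `>x` is a character string. Without an assigned number it cannot be averaged, logged, subtracted from a baseline or compared in a numeric maximum. The results affected are the highest ones, so their absence is informative.

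Two things are at stake. The exploratory biomarker comparisons could understate both levels and treatment differences. Numeric safety displays could also omit the most extreme reading. NT-proBNP is the clearest case, because Protocol section 2.3.1 lists its monitoring as a mitigation for progression of heart failure. The wording also leaves two programmers free to produce different tables from the same data.

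**Working it through.** **Plan's own figures.** The documents give no figure on this point: no upper limits and no expected count of `>x` results. The sample size does not depend on it, but it does reproduce. The standardised difference is 150/(420·√(2/72)) = 150/70 = 2.143. Subtracting 1.282 (one-sided 10%) gives 0.861, hence 80.5% power with 72 per arm. 216/0.95 gives 228 after rounding up.

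**Does the rule reach the models?** Section 3.1.5 speaks of summary statistics, but it adds "Note that 0 should not be used as an imputed value in case the endpoint requires a log transformation". That note matters only if the assigned values go on to log-scale analyses. Among laboratory variables, those are the biomarkers of section 4.2.8.2. So `<x` results enter the models as numbers and `>x` results have nothing to enter.

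**Size, illustration only.** Assumptions, none from the documents: values are log-normal; the placebo log-mean is 0; the log-SD s is 1.0 or 1.5 in both arms; a share q of placebo values (1% or 5%) lies above the limit; the true active/placebo ratio is R. One visit is compared, without baseline adjustment.

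- Log limit: u = s·Φ⁻¹(1 − q). For an arm with log-mean μ, a = (u − μ)/s.
- Mean log if `>x` is dropped: μ − s·φ(a)/Φ(a).
- Mean log if `>x` is set to the limit: μ·Φ(a) − s·φ(a) + u·(1 − Φ(a)).

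Worked case with s = 1.0, q = 5%, R = 0.70, so u = 1.645:

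- Placebo, dropped: −0.1031/0.95 = −0.1086, a geometric mean of 0.897 against a true 1.
- Active: μ = ln 0.70 = −0.3567 and a = 2.0015. Dropped: −0.3567 − 0.0538/0.9773 = −0.4118.
- Ratio, dropped: exp(−0.4118 + 0.1086) = 0.738.
- Set to the limit: placebo −0.0209, active −0.3651, ratio exp(−0.3442) = 0.709.

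Results, dropped / set to limit:

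| Log-SD | Placebo share above limit | Placebo geometric mean (true 1) | True ratio 0.70 reads | True ratio 1.50 reads |
|---|---|---|---|---|
| 1.0 | 1% | 0.973 / 0.997 | 0.711 / 0.702 | 1.444 / 1.489 |
| 1.0 | 5% | 0.897 / 0.979 | 0.738 / 0.709 | 1.359 / 1.454 |
| 1.5 | 1% | 0.960 / 0.995 | 0.713 / 0.702 | 1.451 / 1.491 |
| 1.5 | 5% | 0.850 / 0.969 | 0.742 / 0.710 | 1.369 / 1.460 |

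With R = 1 the ratio is 1.000 under both rules.

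For arithmetic means, as shares of the true mean, dropping gives Φ(u/s − s)/(1 − q). Setting to the limit gives Φ(u/s − s) + q·exp(u − s²/2). Over the same four cases the mean is 8% to 41% too low when values are dropped, and 3% to 25% too low when set to the limit.

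**Numeric maxima.** If a participant's readings are two numbers and one `>x`, a program taking the largest numeric value returns the larger of the two numbers, not the `>x` reading.

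**The case against.** The strongest reply is that the SAP never says `>x` results are excluded. Where section 3.1.5 intends exclusion it says so, as it does for PK values that are not reportable or have no sample. A `>x` result was obtained, so it is not missing in the ordinary sense. This stands to the extent that exclusion is an inference. It does not remove the problem: declining to assign a number has the same effect in any numeric output, and nothing in the SAP supplies another route.

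Two stronger readings are tempting, and the documents do not support them.

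- **That the most allergic participants drop out of the IgE, sensitisation and T2 subgroups.** For sensitisation, section 3.1.7 says "a result equal or greater than 1.41 kU/L and total IgE > 100 kU/L will define sensitisation". A `>x` result satisfies such a cut-off without any number whenever x is at or above it. High T2 by the GINA definition can also be met through eosinophils or FeNO alone.
- **That every reading above the limit vanishes from the maximum-value safety tables.** The haematology, chemistry and urinalysis shift tables use categorical results, and NT-proBNP is also shown as a shift table. A `>x` reading can be classed as high in all of these.

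Other safeguards remain. All laboratory results are listed. Potential Hy's Law cases trigger central-laboratory alerts (Protocol Appendix E) and have an individual-subject table. Cardiac events are of special interest, and LVEF is summarised. The size also rests on assumed inputs, and few `>x` results may occur. These points limit the consequence; they do not supply the missing rule.

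**Conclusion.** The point holds in a limited form. As written, section 3.1.5 gives numbers at the low end and withholds them at the high end. Descriptive statistics, change from baseline, the log-scale biomarker models and numeric safety maxima or plots would then lose the highest results because they are high.

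On the assumptions above, geometric means fall by 2.7% to 15.0%, against 0.3% to 3.1% if the limit is substituted. A true ratio of 0.70 reads 0.71 to 0.74 (0.70 to 0.71 with substitution), and a true 1.50 reads 1.36 to 1.45 (1.45 to 1.49). A true null ratio is not biased when the two arms share the same distribution. The size in this trial cannot be stated, because no upper limits or frequencies are given.

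The main analysis of pre-bronchodilator FEV1 is unaffected, since FEV1 is not a laboratory value. FeNO is a breath test, and PK has its own rules. What remains concerns exploratory biomarkers and some numeric safety displays.

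**What to change.** Replace the sentence on `>x` in SAP section 3.1.5 with:

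> Values of the form >x are set to x (the upper limit of quantification) for summary statistics, MMRM/ANCOVA, numeric maxima and liver figures; they are classed as high in shift tables and as above any cut-off at or below x; >x is shown in listings and the number of such values is footnoted by arm and visit.

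The cost is one SAP sentence and a one-line derivation. The drawback is that x is only a lower bound, so some bias stays, though less than with omission. If the footnoted counts prove material for a biomarker, a censored-data model could be added as a sensitivity analysis. The change should be fixed before the primary analysis data lock, so that the choice cannot depend on the results.

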3.1.5.1 Imputation of partially missing AE dates

Date and time of AE are mandatory eCRF fields. No imputations are expected. In the rare cases of missing date, following rules will be applied. Completely missing AE dates are not imputed.

Partially missing AE end dates are imputed as below:

- If the AE is ongoing, the end date is stated to missing.
- If the AE is not ongoing, and if only the day is missing: Assume the last day of the collected month.
- If the AE is not ongoing, and the month is missing: Assume 31-DEC of the collected year.

After applying these rules, if the imputed AE end date is after the end of study date, the AE end date is set to the end of study date.

Before proceeding with the AE start date imputation, the AE end date are imputed as described above.

Only partial AE start dates are imputed. Dates which are completely missing are not imputed. Partial dates are imputed as described below:

- If the day is missing and:
 - If the month and year are different from the month and year of the first dose of IP, assume 01-MMM-YYYY.

- If the month and year are the same as the first dose of IP month and year and the end date is on or after (including ongoing / missing) the first dose of IP, then assume the date of the first dose of IP.
- If the month and year are the same as the first dose of IP month and year and the end date is prior to the first dose of IP, then assume the end date.
- If the month is missing and:
 - If the year is different from the year of first dose of IP, assume 01-JAN-YYYY of the collected year.
 - If the year is the same as the first dose of IP year and the end date is on or after (including ongoing / missing) the first dose of IP, then assume the date of the first dose of IP.
 - If the year is the same as the first dose of IP and the end date is prior to the first dose of IP, then assume the end date.

After applying these rules, if the imputed AE start date is after a complete AE end date then assume the same date as the complete AE end date; if the end date is missing and the imputed AE start date is after the end of study date then assume the end of study date.

3.1.5.2 Imputation of partially missing medication dates

Both, completely missing and partially missing concomitant medication start dates are not imputed.

Completely missing medication end dates are not imputed. Partially missing concomitant medication end dates are imputed as below:

- If the medication is ongoing, the end date is set to missing.
- If the medication is not ongoing, and if only the day is missing: Impute with the last day of the collected month.
- If the medication is not ongoing, the month is missing: Impute with 31-DEC of the collected year.

After applying these rules, if the imputed date is after the end of study date, the medication end date is set to the end of study date.

3.1.6 Derivation of durations

3.1.6.1 Time since Asthma diagnosis (years)

Time from asthma first diagnosis date to screening will be calculated as (date of first diagnosis of asthma minus date informed consent signed plus one) divided by 365.25.

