3.1.6.2 Age at onset of asthma (years)

Age at onset of asthma will be calculated as the age (years) at screening minus time since asthma diagnosis (Section 3.1.6.1), rounded to the below integer.

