3.1.6.3 Time since Asthma symptoms started (years)

Time from asthma first symptoms date to screening will be calculated as (date of first symptoms of asthma minus date informed consent signed plus one) divided by 365.25.

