3.1.6.4 Time since last exacerbation (months)

Time since last asthma exacerbation date to screening will be calculated as (date of most recent exacerbation minus date informed consent signed plus one) divided by 365.25 and multiplied by 12.

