3.1.6.6 Time from first IP administration to AE onset (days)

Time from first IP administration to AE onset will be calculated as date of AE onset minus date of first IP administration plus one.

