3.2.1.1 Demographics and subject-specific characteristics

Demographic and subject characteristics include age, age group ($\geq 18 - < 50$; $\geq 50 - 65$), age group for EudraCT reporting purpose ($\geq 18 - < 65$; ≥ 65), sex, race, ethnic group, country, height (cm), weight (kg), body mass index (BMI) (kg/m^2), previous treatments containing ICS and combination of products containing ICS, asthma characteristics at baseline. Age in years will be used as provided in the IWRS (Interactive Web Response System). BMI (kg/m^2) is calculated as described in Section 3.5.2.

Height, weight and BMI are allocated to the analysis visits as per Section 3.1.4. Evaluations with missing or partially missing dates cannot be imputed to any analysis visit. Only baseline values are included in the demographic and subject characteristics.

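### Minor SAP correction: reversed dates give an asthma onset age never below current age, and zero exacerbations in 12 months has no subgroup level; the primary analysis is unaffected

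*SAP*

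**What the plan says.** **Durations.** SAP 3.1.6.1 opens with "Time from asthma first diagnosis date to screening will be calculated as" and then gives the numerator as "date of first diagnosis of asthma minus date informed consent signed plus one". SAP 3.1.6.3 uses "date of first symptoms of asthma minus date informed consent signed plus one" and SAP 3.1.6.4 uses "date of most recent exacerbation minus date informed consent signed plus one", the latter scaled to months. The on-study durations in 3.1.6.6 to 3.1.6.9 run the other way, for example "date of AE onset minus date of first IP administration plus one".

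**Onset age.** SAP 3.1.6.2 states: "Age at onset of asthma will be calculated as the age (years) at screening minus time since asthma diagnosis", with the result "rounded to the below integer". On age itself, SAP 3.2.1.1 says "Age in years will be used as provided in the IWRS", without saying whether that is completed years.

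**Use.** The three durations and onset age are summarised in the baseline asthma table (SAP 4.2.3.4; Table 14.1.7.3). Onset age, split at the median, is a subgroup factor in SAP 3.1.7. Each such factor gets its own MMRM of the primary endpoint (SAP 4.2.4.3) and appears in the forest plot (Figure 14.2.1.4).

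**Exacerbation history.** Protocol inclusion criterion 19 asks for at least one exacerbation in the 24 months before SV1. The eCRF item in SAP 3.2.1.4 counts the 12 months before screening. SAP 3.1.7 groups that count as 1 vs ≥ 2 and excludes only participants whose subgroup value is missing. SAP section 6 names protocol Amendment V4.0 as its basis.

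**The concern.** Diagnosis, first symptoms and last exacerbation all precede consent in the ordinary case. Subtracting the consent date from them gives a negative time since the event. Onset age then adds the disease duration to current age instead of removing it.

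Protocol inclusion criterion 2 requires asthma to have developed before age 25, so the derived value contradicts eligibility for everyone aged 25 to 64. Impossible ages would be visible in the baseline table. The subgroup, however, is labelled only as below or at/above the median, so its forest plot row would look normal while showing something close to an age split. Age is already a separate subgroup factor, and onset age is of scientific interest because the protocol (4.2, 4.2.2) builds its population on early-onset disease.

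On the second item, a participant whose only exacerbation was more than 12 and up to 24 months before SV1 is eligible and has a valid recorded count of 0. That count belongs to neither level, and because it is not missing, the exclusion rule does not cover it.

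**Working it through.** **1. The plan's own figure.** With 72 per arm, difference 150 mL and SD 420 mL, the standard error is 420 × √(2/72) = 70 mL. Then 150/70 = 2.143, less 1.282 for one-sided 10%, leaves 0.861, which is 80.5% power against the stated 80% or more. Allowing 5%: 216/0.95 = 227.4, so 228. Neither onset age nor exacerbation count is a term in the MMRM of SAP 4.1.2, so these figures do not move.

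**2. Onset age as written.** Let A be the age used and g the days from diagnosis to consent.

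- Time since diagnosis = (−g + 1)/365.25.
- Onset age = floor(A − that) = floor(A + (g − 1)/365.25).

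Criterion 2 requires diagnosis more than 12 months before SV1. Over every whole age from 18 to 64 and every g of at least 330 days, the smallest value of derived onset minus current age is 0.

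| True age, age at diagnosis | As written | Dates swapped, completed-years age | Dates swapped, unrounded age |
|---|---|---|---|
| 64.9, 0.3 | 128 | – | – |
| 45.5, 12.3 | 78 | 11 | 12 |
| 40.8, 0.4 | 80 | −1 | 0 |
| 18, 366 days before consent | 18 | – | – |

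For example, 45 + 33.2 − 1/365.25 = 78.2, which gives 78. With unrounded age the first row becomes 64.9 + 64.6 = 129.5, less one day, which gives 129.

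**3. Time since last exacerbation as written.** Exclusion criterion 22 puts the last event at least 56 days before SV4. Consent at SV1 is 28 to 35 days before SV4, so the shortest gap is 21 to 28 days: (−21 + 1)/365.25 × 12 = −0.66 months, or (−28 + 1)/365.25 × 12 = −0.89. At 24 months, (−730 + 1)/365.25 × 12 = −23.95. Values nearer 0 need consent before SV1, which Table 1 footnote a of the protocol allows.

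**4. Effect on the median split.** The documents give no age or onset distribution, so five were assumed: 2 million draws each, onset below 25, diagnosis more than one year before consent, and diagnosis taken as onset as in SAP 3.1.6.2. The last two columns describe the result if only the dates are swapped and age is in completed years.

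| Age; onset (years) | Agrees with true onset split | Agrees with current-age split | One year too low | −1, among onset < 1 |
|---|---|---|---|---|
| U(18,65); U(0,25) | 0.446 | 0.931 | 0.504 | 0.506 |
| N(45,12) clipped to 18–65; U(0,25) | 0.402 | 0.897 | 0.523 | 0.521 |
| U(18,65); 25·Beta(1,2) | 0.451 | 0.946 | 0.510 | 0.504 |
| U(18,65); 25·Beta(2,1) | 0.469 | 0.945 | 0.499 | 0.352 |
| U(30,60); U(0,25) | 0.397 | 0.896 | 0.502 | 0.503 |

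A separate run at n = 228 with three onset distributions put 55–57% of participants in the wrong half, in line with the first column.

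**5. Why a swap alone is not enough.** Completed-years age already drops the fraction of a year since the last birthday. Subtracting an exact duration and rounding down drops it a second time, so about half of participants lose a year. With unrounded age the error falls to 0.26–0.29%, the residue of the added day.

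**6. Exacerbation count.** Criterion 19 allows 0 in the last 12 months, and the levels are 1 and ≥ 2. How many participants have 0 cannot be derived from the documents. A separate level for 0 would need 0.20 × 228 = 45.6, that is 46 participants, to meet the 20% rule in SAP 3.1.7.

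**The case against.** The strongest reply is that the reversal corrects itself. The heading and first clause of 3.1.6.1 state the intended direction, the on-study durations are ordered correctly, and literal code would print negative durations and onset ages above 100 in a table someone will read. This is fair as to intent and is why the point is minor. It does not make the operative text right.

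Second, the rounding problem depends on IWRS age being in completed years, and it hardly touches the subgroup result. After a date swap alone, the median split agrees with the true whole-year onset split for 97–98% of participants in the same scenarios, and values of −1 make up about 0.1–4% of everyone. That stands: the rounding mainly shifts one descriptive row by about half a year on average.

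Third, diagnosis dates may be decades old and partial, and SAP 3.1.5.1 and 3.1.5.2 impute only adverse event and medication dates. If only the year were known and 1 January were used (an assumption), about half of onset ages would still be wrong with unrounded age. That also stands, so the 0.3% figure holds only for complete dates.

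Fourth, criterion 2 limits when asthma developed, while SAP 3.1.6.2 uses the diagnosis date. Documentation route (c) does not require a diagnosis before 25, so a genuine diagnosis age of 25 or more is conceivable. It would not explain such a value in every participant aged 25 to 64. The early-onset rationale is also stated for eligibility, not for the median split.

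On the exacerbation count, zeros arise only among participants entered under the 24-month criterion, and leaving them out of one exploratory factor would do little harm. The SAP still gives no rule. Pooling 0 with 1 is one choice; a separate level or an explicit exclusion would also close the gap.

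**Conclusion.** The point holds and is minor. As written, three durations have the wrong sign and derived onset age is never below current age (18 to 128 with completed-years age, up to 129 unrounded). Four rows of the baseline asthma table would be wrong. The onset-age subgroup MMRM and its forest plot row would mostly reflect current age: 90–95% agreement with a current-age split and 40–47% with the true onset split, under the five assumed distributions. A valid count of 0 exacerbations has no level in a second exploratory factor, for an unknown number of participants.

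The primary MMRM, type I error, power (80.5%) and sample size do not change. The lower bound on derived onset age relies on criterion 2 being met. The one-year error after a simple date swap relies on IWRS age being in completed years, which the SAP does not state. Redacted subgroup definitions could not be checked.

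**What to change.** - **SAP 3.1.6.1 and 3.1.6.3:** use (consent date − event date + 1)/365.25. **SAP 3.1.6.4:** the same order, × 12.
- **SAP 3.1.6.2:** derive onset age from diagnosis date and birth date if birth date is collected, otherwise from unrounded age at consent. Round down only as the last step. State whether IWRS age is in completed years, and how partial diagnosis dates are handled.
- **SAP 3.1.7:** define the exacerbation factor as ≤ 1 vs ≥ 2 in the last 12 months, so that every recorded count has a level without creating a stratum that may fail the 20% rule.

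The cost is SAP wording and small programming changes, best made before the baseline and subgroup outputs are programmed. The event dates and the 12-month count are already collected. The documents do not say whether birth date or unrounded age is held.
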